1. Is there increased activation of STAT proteins in peripheral blood in patients who relapse?

The direct molecular targets of cytokine-induced JAK tyrosine kinases are the signal transducers and activators of transcription (STAT) proteins, which when phosphorylated become activated and translocate to the nucleus to bind DNA and induce cytokine specific gene expression and chromatin regulation⁵. STAT proteins are key molecular regulators of CD4-T-helper (Th) cell lineage differentiation programmes, which are directed and propagated following specific signature cytokine cues⁶. Aberrant activation of STATs is, thus, often a critical step in the molecular pathogenesis of several inflammatory and auto-immune diseases, that are associated with dysregulated Th function^{7,8}. Of the 7 STAT proteins, increased activation of STAT1, STAT3, and STAT5a/b in particular, and to a lesser extent STAT4 and STAT6, have been associated with the pathophysiology of UC, consistent with their activation by inflammatory cytokines involved in UC pathogenesis, such as IFNγ, IL12 (TH1), IL4, IL6, IL13, IL21 (TH2), IL6, IL23 (TH17), IL9 (TH9)⁹⁻¹³. Therefore, we will monitor the phosphorylation of STAT proteins in PBMC from patients enrolled in the study, with blood drawn before dose reduction.

2: Are there changes in cytokine expression in peripheral T cells that predict relapse?

The immunopathogenesis of IBD, including UC, is driven by the dysregulated expression of specific proinflammatory cytokines, secreted primarily by CD4 T-effector cells, which critically drives inflammation and tissue destruction¹⁴. These cytokines mediate their actions via STAT proteins, which are the subject of evaluation in question 1 above. To understand if there are changes in cytokine expression that predict relapse in specific patients, we will evaluate cytokine expression in peripheral CD4 T cells. The cytokines we will study are the key CD4 T-effector cytokines IFN γ , IL17, and IL9 corresponding to TH1, Th17 and Th9 lineages, that have been implicated in the pathogenesis of UC. These data will inform us of any changes in peripheral levels of pathogenic cytokines that predict patients who will relapse following tofacitinib dose reduction.

3: Can we identify signature gene(s) that serve as a biomarker to predict relapse?

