7.1 Study Design

This is a prospective observational study. We will prospectively enroll a cohort of 50 UC patients who have achieved an adequate response to tofacitinib at a dose of 10mg bd and whose dose is being reduced to 5mg bd following a routine flexible sigmoidoscopy. Colonic

tissue and blood samples will be collected at study entry, and patients' disease course will be followed-up through routine care.

Week 44 has been chosen for the primary endpoint, as 44 weeks post dose de-escalation was used as the endpoint in OCTAVE Sustain.

Primary endpoint:

• Biomarkers, clinical markers and histological markers associated with ongoing treatment with 5mg bd in the absence of steroids at week 44.

Secondary Endpoints

• Biomarkers, clinical markers and histological markers associated with steroid free endoscopic remission at routine endoscopy at week 44

Biomarkers / outcome measures will include:

- Clinical status (SCCAI)
- CRP and faecal calprotectin (as part of routine care)
- Histological markers of disease activity (Nancy histological index) (as part of routine care)
- STAT activation in peripheral blood mononuclear cells
- Cytokine expression in peripheral T cells
- Gene signatures in colonic biopsies

Guy's and St Thomas' MHS

NHS Foundation Trust

Flow Diagram

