13.1 Data to be collected

Data will be collected by the study investigators.

Data at the various time points include:

- Baseline:
 - Demographic data, disease extent history, concomitant medications, previous IBD medications, smoking history from patient history and notes.
 - Simple Clinical Colitis Activity Index (SCCAI), calculated by the assessor •
 - Serum CRP and albumin, and faecal calprotectin
 - Endoscopic Mayo Score, recorded by the endoscopist
 - Nancy histological index, reported by the pathologist •
 - STAT activation in peripheral blood mononuclear cells, recorded from • laboratory data
 - Cytokine expression in peripheral T cells, recorded from laboratory data
 - Gene and T/B cell receptor analysis in colonic biopsies, recorded from laboratory data
- Flare
 - Time point, alteration to treatment, faecal calprotectin, CRP, SCCAI, endoscopic Mavo score (if endoscopy performed), all recorded by the investigator from the patient notes.
 - Gene signatures in colonic biopsies, recorded from laboratory data
- Week 44
 - CRP, albumin, SCCAI, calprotectin, recorded from the patient's notes. •
 - Endoscopic Mayo score, recorded by the endoscopist
 - Nancy histological index, reported by the pathologist
 - STAT activation in peripheral blood mononuclear cells, recorded from laboratory data
 - Cytokine expression in peripheral T cells, recorded from laboratory data
 - Gene signatures in colonic biopsies, recorded from laboratory data

In the event of incomplete data, patients will be telephoned to arrange completion.

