13.2 Data handling and record keeping

Pseudo-anonymised patient data will be kept on a password-locked computer. Every patient will be appointed a two-digit study number. All patient specific data will be recorded using only this number. The full name and birth date will only be recorded on the informed consent form. The study coordinator will monitor patient inclusion and protocol steps, coordinate data entry, perform data analyses and reporting. Data will be double entered into a Microsoft Excel spreadsheet to endure validity and quality.

All trial data will be stored in line with the Data Protection Act (1998). Records will be retained for a maximum of 7 years.

14 Statistical considerations

14.1 Sample size calculation (some pilot/feasibility studies may not require a formal sample size calculation)

Given the endpoints are exploratory, sample size calculations are not possible.

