14.2 Statistical analysis

[name], clinical research fellow in gastroenterology, will perform the statistical analyses.

Baseline variables will be presented as either mean and standard deviation or medians and inter quartile range, depending on the normality of the data.

Receiver operator curves will be generated to determine optimal cut-offs for continues variables, predictive of disease flare.

Kaplan-Meier curves will be generated to allow comparisons of subdivisions of patients based on genetic and biochemical variables, using determined cut-offs.

Univariate and Multivariate analyses will be performed on clinical, biochemical and genetic variables to establish predictors of disease flare.

15 Ethical considerations

This is a non-interventional, observational study. Approvals will be sought from REC and HRA. Patients will need to provide informed consent to participate, and the only data collected from patients which occur in addition to standard of care are the additional tissue and blood samples collected at baseline and at week 44 for genetic, immune cell and cytokine analyses. Decisions regarding patient's care will have no relation to the study and will be directed by the patient's care team. Data collection and monitoring will occur in accordance with the rules and regulations set out above. The study design, management, undertaking, analysis and dissemination of results have had patient involvement, via a patient representative who sits on our project approvals board.

16 Financing and Insurance

Guy's and St Thomas' NHS Foundation Trust will take primary responsibility for ensuring that the design of the study meets appropriate standards and that arrangements are in place to ensure appropriate conduct and reporting are adhered to. King's College London as co-sponsor also provides cover under its No Fault Compensation Insurance, which provides for payment of damages or compensation in respect of any claim made by a research subject for bodily injury arising out of participation in a clinical trial or healthy volunteer study (with certain restrictions).

17 Reporting and dissemination

It is intended that the results of the study will be reported and disseminated at international conferences and in peer-reviewed scientific journals. A manuscript of the final study results will be submitted to an IBD specific journal (IBD or JCC) or to the IBD section of a general gastroenterology journal (Gut, Gastroenterology or CGH).

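### With 50 patients and 20 or more candidate markers, the Section 14.2 analysis can nominate candidate predictors of flare but cannot establish them, and the precision that Section 14.1 implies is beyond calculation can be computed

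*Protocol*

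**What the plan says.** - **Size.** Section 7.1: "We will prospectively enroll a cohort of 50 UC patients". Section 14.1 gives no justification: "Given the endpoints are exploratory, sample size calculations are not possible".
- **Analysis and aim.** Section 14.2: "Univariate and Multivariate analyses will be performed on clinical, biochemical and genetic variables to establish predictors of disease flare". ROC curves are to supply cut-offs for individual continuous variables, and these cut-offs then define the Kaplan-Meier groups.
- **Candidates.** Section 13.1 lists "Demographic data, disease extent history, concomitant medications, previous IBD medications, smoking history from patient history and notes" and "Serum CRP and albumin, and faecal calprotectin", along with SCCAI, endoscopic Mayo score, Nancy index, STAT activation, T-cell cytokines and gene analysis. Section 5 says which STAT proteins are of interest: "increased activation of STAT1, STAT3, and STAT5a/b in particular, and to a lesser extent STAT4 and STAT6". Section 10.3 measures IFNγ, IL17 and IL9 by intracellular staining and again by ELISA. It adds a multiplex plasma array (analyte number not given) and RNA sequencing. Section 5 also adds mucosal flow cytometry.
- **Validation.** The only step given that name is qPCR of the top 5–10 genes (Section 10.3). No patients outside the cohort are named for it.

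**The concern.** The protocol calls its endpoints exploratory when explaining why it has no sample size calculation, and then sets the analysis the task of establishing predictors. Those positions conflict. With roughly one flare or fewer per candidate marker, some markers will often look predictive by chance, and a model built from them will often appear to discriminate. Section 6 hopes that the findings will eventually help decide who stays on the higher dose. A chance finding reported as an established predictor could therefore mislead later work.

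Section 14.1 has a separate error. An exploratory aim does not prevent a calculation of what 50 patients can show. Precision can be computed, and a reader needs it to judge the results.

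**Working it through.** The protocol states no power, alpha or flare rate, so there is no figure of its own to reproduce.

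**Inputs**
- N = 50 (Section 7.1).
- Flares: not stated. Assumed 15, 20 or 25 (30%, 40% or 50% of 50).
- Alpha: not stated. Assumed 0.05, two-sided.
- Candidates: about 6 history items (age, sex, extent, concomitant drugs, previous drugs, smoking; reading age and sex into demographic data), 6 routine markers (SCCAI, CRP, albumin, calprotectin, Mayo, Nancy), at least 5 STATs, and 3 cytokines by flow cytometry. 6 + 6 + 5 + 3 = 20. Counting the 3 ELISA repeats gives 23. A list of 30 stands for the case where some array or mucosal markers are added.

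**Step 1. Events per candidate.** With 20 candidates: 15/20 = 0.75 to 25/20 = 1.25.

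**Step 2. Chance findings one marker at a time (no true predictor, independent markers).**
- 20 candidates: expected false positives 20 × 0.05 = 1.0; chance of at least one, 1 − 0.95^20 = 0.64.
- 30 candidates: 30 × 0.05 = 1.5; 1 − 0.95^30 = 0.79.

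**Step 3. Joint model on pure noise.** Simulated with n = 50, normal markers, a t-test screen at p<0.10 and then logistic regression, with AUC measured on the same data. The screen and its threshold are assumptions. The median is over runs in which at least one marker passes; the last two columns count all runs. Ranges cover 15–25 flares.

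| Candidates | Median apparent AUC, independent | AUC ≥0.70, independent | AUC ≥0.70, correlation 0.5 |
|---|---|---|---|
| 20 | 0.73–0.75 | 59–64% | 27–37% |
| 30 | 0.77–0.79 | 79–84% | 38–45% |

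A repeat with 1,500 runs per setting agreed closely for independent markers. At correlation 0.5 it gave 25–32% and 36–44%, so read that column as roughly a quarter to under a half. In comparable runs with 24 markers, the AUC of such models on new data was 0.50.

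**Step 4. Without a screen.** Entering 24 noise markers together gave a mean apparent AUC of 0.94–0.97, so the conclusion does not depend on the assumed screen.

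**Step 5. Precision at n = 50.** Hanley-McNeil variance, with A = 0.70, n1 flares and n0 = 50 − n1:

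Var = [A(1−A) + (n1−1)(A/(2−A) − A²) + (n0−1)(2A²/(1+A) − A²)] / (n1·n0)

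Here A/(2−A) − A² = 0.0485 and 2A²/(1+A) − A² = 0.0865.
- 20 flares: (0.21 + 19 × 0.0485 + 29 × 0.0865)/600 = 0.00606; SE 0.078; half-width 1.96 × 0.078 = 0.153.
- 15 flares: half-width 0.167. 25 flares: 0.146.

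A single marker fixed in advance, with a true AUC of 0.70, would thus carry a 95% interval of about 0.55 to 0.85 at 20 flares.

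**Step 6. The qPCR step.** It re-measures the top-ranked genes by another method. With no other patients named, agreement would confirm the measurement and not the prediction.

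**The case against.** **The text does not describe a screen.** Section 14.2 names univariate and multivariate analyses without saying that one feeds the other, sets no screening threshold, and plans ROC curves only for cut-offs of single variables. A reader might infer that markers will be screened and that the combined model's AUC will be reported. The protocol does not say so. This stands, which is why Step 3 is conditional. Steps 1, 2 and 5 need neither assumption.

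**The transcriptome.** A reader might infer that thousands of genes enter the multivariate model. Section 14.2 refers only to genetic variables, and Section 10.3 gives RNA sequencing its own pipeline. The figures above therefore leave it out.

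**Independence.** Section 5 says that the cytokines act through the STAT proteins, so correlation is to be expected, and ELISA repeats cytokines already measured. A reader might infer that noise would always look good under this plan. The correlated runs do not support that: often, or sometimes, is the fair word.

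**A SAP may exist.** Shrinkage, resampling and false discovery control are commonly specified there, so their absence from the protocol is not the finding. But a SAP cannot add flares or an independent cohort, and it does not correct the aim in 14.2 or the statement in 14.1.

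**Intent.** The protocol is openly exploratory in places, hopes only for eventual use in dosing, and separates care decisions from the study (Section 15). A reader should not infer that this study's results will directly set treatment. The heading of 14.1 also allows that pilot or feasibility studies may not need a formal calculation, and Section 8 expects about 50 eligible patients a year, so 50 is plausibly a feasibility number. That would be a fair reason to give. It does not make a calculation impossible.

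**Conclusion.** The point holds in a limited form. The aim in 14.2 claims more than 50 patients and an open list of 20 or more candidates can deliver, and it conflicts with the exploratory status claimed in 14.1. The statement in 14.1 is incorrect as written.

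The size rests on 15–25 flares, alpha 0.05 and a candidate count of 20–30, none of which the protocol fixes. Under independence a chance finding is more likely than not; under strong correlation it remains a substantial possibility. The AUC figures rest further on an assumed screen and on logistic models. The protocol does not show that the study will mistake noise for signal: a SAP could provide honest performance estimates. Even then, the result would be a set of candidates for testing in other patients.

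**What to change.** **Section 14.2**
1. Change the aim from establishing predictors to nominating candidate predictors, and bring the expectation in Section 5 about usable genes into line.
2. List the non-transcriptomic candidates, including the array analytes, and apply Benjamini-Hochberg false discovery control across that list.
3. Limit any multivariable model to a few terms fixed in advance, or use shrinkage. The choice of terms or penalty is for the investigators.
4. Report model performance only after bootstrap or cross-validation that repeats every selection and cut-off step. In the noise simulations with 24 markers, cross-validation with selection repeated inside each fold returned an AUC of about 0.48–0.50, as it should.
5. Say that the qPCR step checks the measurement unless it uses patients outside the cohort.

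**Section 14.1.** Replace the statement with the reason for choosing 50 and a precision statement under named assumptions, for example: for a marker with a true AUC of 0.70, the 95% half-width is about 0.15–0.17 with 15–25 flares in 50 patients.

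**Cost.** Wording and standard software, with no new patients or samples. Fewer markers will be declared and performance figures will be less favourable. The loss of power is real. Under Bonferroni over 24 markers, which is stricter than the control proposed here, power to separate flare rates of 20% and 60% in a 25/25 split falls from 85% to 42%. That is a further reason to keep the candidate list short.
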